Withdrawal of consent: If consent is withdrawn, the subject will not receive any further investigational product or further study observation. Note that the subject may need to undergo additional tests or tapering of treatment to withdraw safely.

Lost to follow-up: Subjects will be considered lost to follow-up only if no contact has been established by the time the study is completed such that there is insufficient information to determine the subject's status through end of study (defined as 1 year after the final subject is entered into the study or the date the study is closed by the sponsor).

- Note: Subjects refusing to return to the site or to continue participation in the study should be documented as “withdrawal of consent” rather than “lost to follow-up.” Investigators should document attempts to re-establish contact with missing subjects throughout the study period. If contact with a missing subject is re-established, the subject should not be considered lost to follow-up and any evaluations should resume according to the protocol.

Permanent discontinuation of investigational product: Subjects who are permanently discontinued from further receipt of investigational product, regardless of the reason (withdrawal of consent, due to an AE, other), will be identified as having permanently discontinued treatment. Subjects who permanently discontinue treatment may either be considered to have completed the study or not to have completed the study (see Section 4.6).

Subjects who are permanently discontinued from receiving investigational product will be followed for safety through the full study period through 30 days after the last administration

of MEDI-565, including the collection of any protocol-specified blood or urine specimens, unless consent is withdrawn, lost to follow-up, or enrolled in another clinical study. In addition, subjects will be followed for disease evaluations every 3 months (\pm 2 weeks) until disease progression, death, initiation of alternative anticancer treatment, withdrawal of consent, or end of study (defined as 1 year after the last subject begins treatment or the date the study is closed by the sponsor), and for survival every 3 months until death, withdrawal of consent, or end of study.

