5.2 Schedule of Study Procedures

All subjects who are assigned an SID number and receive any investigational product will be followed according to the protocol regardless of the number of doses received, unless consent is withdrawn. The investigator must notify the sponsor or designee of deviations from protocol visits or evaluations and these evaluations, if applicable, must be rescheduled or performed at the nearest possible time to the original schedule. Protocol deviations will be recorded on the source document with an explanation for the deviation and the investigator must comply with the applicable requirements related to the reporting of protocol deviations to the IRB/IEC.

Subjects/legal representatives will be instructed to call study personnel to report any abnormalities during the intervals between study visits and to come to the study site if medical evaluation is needed and the urgency of the situation permits. For emergency and other unscheduled visits to a medical facility other than the study site, medical records will be obtained by the investigator and made available to the sponsor or designee during monitoring visits.

For cycle 2 or greater, the start of the cycle may be delayed for up to 7 days to accommodate scheduling.

A schedule of study procedures is presented in [Table 5.2-1](#) and [Table 5.2-2](#) followed by a description of each visit. A description of the study procedures is included in Section [5.3](#).

Table 5.2-1 Schedule of Subject Evaluations: Screening and Treatment Periods

Procedure	Screening	Cycle 1								Cycle 2 and Every Cycle Thereafter								
		Day -30 to Day -1	Day 1	Day 2	Day 3	Day 4	Day 5	Day 8	Day 15	Day 22	Day 1	Day 2	Day 3	Day 4	Day 5	Day 8	Day 15	Day 22
Written informed consent & HIPAA/assignment of SID	X																	
Verify eligibility criteria	X	X																
Medical history	X																	
Hepatitis B, C	X																	
HIV-1, HIV-2	X																	
Serum β HCG	X																	
Urine or Serum β HCG		X								X								
Mini-Mental State Exam and gait assessment	X	X	X	X	X	X	X	X	X	X					X	X	X	
MEDI-565 administration		X	X	X	X	X				X	X	X	X	X				
Dexamethasone prophylaxis		X																
Toxicity monitoring		X	X	X	X	X				X	X	X	X	X				
Physical examination	X	X								X								
Height	X																	

Table 5.2-1 Schedule of Subject Evaluations: Screening and Treatment Periods

Procedure	Screening	Cycle 1								Cycle 2 and Every Cycle Thereafter								

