5.2.3 Post-Treatment Follow-up Period

5.2.3.1 30 Days (plus or minus 3 Days) Post-treatment

This visit is only required for subjects who discontinue treatment for a reason other than disease progression.

- 1) Perform physical examination
- 2) Record weight
- 3) Record vital signs and pulse oximetry
- 4) Record ECG
- 5) Assess Karnofsky Performance Status
- 6) Perform Mini Mental State Exam and gait assessment
- 7) Assess for AEs and SAEs
- 8) Update concomitant medications
- 9) Collect blood samples for post-treatment follow-up:
 - Serum chemistry (including soluble CEA)
 - Hematology
 - Coagulation parameters
 - Concentrations of MEDI-565
 - Anti-MEDI-565 antibodies
 - Circulating tumor cells
 - Flow cytometric analysis
 - Circulating cytokines
 - Circulating soluble protein biomarkers
- 10) Collect urinalysis sample
- 11) Perform CXR, CT or MRI scan (only required for subjects who discontinued treatment without progressive disease and who have not initiated alternative anticancer therapy)

5.2.3.2 3 Months Post End of Treatment

- 1) Perform physical examination (only for subjects who discontinued treatment without progressive disease and who have not initiated an alternative anticancer therapy)
- 2) Record subsequent anticancer therapy

- 3) Record survival status
- 4) Collect blood samples for post-treatment follow-up
 - Complete blood count (CBC) (performed only at 3 months post-treatment)
 - Flow cytometric analysis (performed only at 3 months post-treatment)
- 5) Perform CXR, CT, or MRI scan (only for subjects who discontinued treatment without progressive disease and who have not initiated an alternative anticancer therapy)

5.2.3.3 6 Months and Every 3 Months (plus or minus 7 Days) Post-treatment

This visit may be conducted by telephone if CXR, CT, or MRI scan is not completed. Visits every 3 months post-treatment should be continued until disease progression is documented.

- 1) Record subsequent anticancer therapy
- 2) Record survival status
- 3) Perform CXR, CT, or MRI scan (only for subjects who discontinued treatment without progressive disease and who have not initiated an alternative anticancer therapy)

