5.3.7 Disease Evaluation and Methods

Survival will be followed approximately every 3 months beginning at 3 months post-treatment by clinic visit or telephone (beginning at 6 months post-treatment) until the end of the study.

Tumor measurements and assessments will be based on RECIST v 1.1 ([Eisenhauer et al, 2009](#)) and will be performed at time points as specified in [Table 5.2-1](#) and [Table 5.2-2](#). Additional tumor measurements may be performed at the discretion of the investigator or according to institutional practice. In subjects who achieve a complete or partial response to treatment, tumor measurements will be repeated for confirmation at least 4 weeks later using the same imaging tests. The same tumor assessment method should be used throughout the study.

Tumor measurements must be recorded in metric notation by use of a ruler or calipers, and the same method/technique of tumor assessment must be used throughout the study.

Imaging-based evaluation is preferred to evaluation by clinical examination when both methods have been used to assess the antitumor effect of the treatment. The analysis for tumor response will be based on the investigator's assessment during the conduct of the study.

Tumor assessments may include the following evaluations: physical examination, CXR, CT, or MRI scan of the chest, abdomen, and pelvis, and CT or MRI scan of the brain. CT or MRI scan of the brain will be performed if the subject is neurologically symptomatic. The same method must be used for all subsequent tumor assessments.

- **Physical examination.** Lesions detected by physical examination will only be considered measurable if superficial, eg, skin nodules and palpable lymph nodes. Documentation by color photography including ruler is recommended for estimating the size of skin lesions.
- **Chest x-ray.** Lesions considered acceptable for measurement on chest radiograph should be clearly defined and surrounded by aerated lung. However, CT is preferable.
- **CT scans of the chest, abdomen, and pelvis.** CT scans should be performed with contiguous cuts in slice thickness of 10 mm or less. Spiral CT should be performed using a 5-mm contiguous reconstruction algorithm.

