Progression-free survival will be measured from the start of treatment with MEDI-565 until the documentation of disease progression or death due to any cause, whichever occurs first. Disease progression is defined according to RECIST guidelines. Progression-free survival will be censored on the date of last tumor assessment documenting absence of tumor progression for subjects who have no documented progression and are still alive prior to data cutoff, dropout, or the initiation of alternate anticancer treatment. Subjects having no tumor assessments after the start of treatment with MEDI-565 will have PFS censored on the first date of treatment with MEDI-565. PFS will be evaluated using the Kaplan-Meier method ([Kaplan and Meier, 1958](#)).

Overall Survival

Overall survival will be determined as the time from the start of treatment with MEDI-565 until death. For subjects who are alive at the end of study or lost to follow-up, OS will be censored on the last date when subjects are known to be alive. The OS will be evaluated using the Kaplan-Meier method ([Kaplan and Meier, 1958](#)).

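### Section 4.2.3 codes mere refusal of site visits as withdrawal of consent, which ends follow-up and discards survival and adverse-event information still obtainable by telephone or from records

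*Protocol*

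**What the plan says.** The rule is a note under the lost-to-follow-up paragraph of Protocol 4.2.3: "Subjects refusing to return to the site or to continue participation in the study should be documented as" withdrawal of consent.

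The same section sets out what that code does:
- Observation: "If consent is withdrawn, the subject will not receive any further investigational product or further study observation".
- Safety follow-up to 30 days after the last administration continues "unless consent is withdrawn, lost to follow-up, or enrolled in another clinical study".
- Subjects off treatment are followed "for survival every 3 months until death, withdrawal of consent, or end of study".

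Elsewhere the protocol accepts that survival status does not need a clinic visit. Section 5.3.7 has it collected "by clinic visit or telephone (beginning at 6 months post-treatment) until the end of the study". Section 5.2.3.3, which covers the contacts from 6 months onward, says: "This visit may be conducted by telephone if CXR, CT, or MRI scan is not completed". Section 5.2.3.2, the 3-month contact, has no such sentence.

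The OS rule in 7.3.2.3 reads: "For subjects who are alive at the end of study or lost to follow-up, OS will be censored" at the last date known alive. It does not mention withdrawal of consent.

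**The concern.** The note puts two different decisions under one code. Someone who refuses all further participation has withdrawn. Someone who will not travel, but would answer a call or let records be consulted, has not. Because the note joins the two with *or*, refusing to travel is sufficient by itself.

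Two sets of data are at stake. The first is overall survival: in advanced disease with no standard therapy, unwillingness to travel plausibly goes with decline, so censoring at that point would not be independent of death. The second is the primary safety endpoint in 7.3.1, AEs and SAEs through 30 days after the last dose, for which scheduled collection stops. Analysis cannot repair either, because the data are never collected.

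**Working it through.** **1. Where the note bites.** A subject reached by a permitted call is not refusing anything, so the question is which contacts lack a telephone route.

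| Stage | Telephone route in the protocol | What a call or records could supply |
|---|---|---|
| Treatment, including Cycle 1 Days 8, 15 and 22 | No scheduled call; subjects "will be instructed to call study personnel to report any abnormalities during the intervals between study visits" (5.2) | Symptoms and events; not laboratory tests, vital signs or oximetry |
| 30-day visit (5.2.3.1) | None | AEs, SAEs, concomitant medication |
| 3-month contact (5.2.3.2) | None | Survival status, later anticancer therapy |
| 6 months onward (5.2.3.3, 5.3.7) | Yes, if no scan is done | Survival status, later anticancer therapy |

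The gap is the first three rows. It carries forward, because a subject coded as withdrawn there never reaches the 6-month call.

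**2. Reachable against missing subjects.** Under 4.2.3 a missing subject is declared lost only if there is still no contact when the study is completed, and evaluations resume if contact is re-established. No such route is given for a reachable subject coded as withdrawn for declining visits. The reachable subject is thus followed less than the missing one.

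**3. OS censoring.** Section 7.3.2.3 names two groups: alive at end of study, and lost to follow-up. The note steers these subjects away from the lost-to-follow-up code, and their status at end of study is not known. They fit neither group.

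**4. Cycle 1.** A subject is evaluable after all five infusions plus safety follow-up over Days 6-28, or on any DLT (4.5.4.2). One who is discontinued in that period without a DLT is replaced (4.2.4). The only stated figure this touches is Table 7.5-1. With P(escalate) = (1−p)³ + 3p(1−p)²·(1−p)³, true rates of 10% to 90% give 0.906, 0.709, 0.494, 0.309, 0.172, 0.082, 0.032, 0.009 and 0.001, so the table reproduces.

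If a share m of subjects with a DLT left before it was recorded and were replaced, the apparent rate would be p(1−m)/(1−pm). At p = 0.40:
- m = 10%: 0.36/0.96 = 0.375, P = 0.35
- m = 25%: 0.30/0.90 = 0.333, P = 0.43
- m = 50%: 0.20/0.80 = 0.25, P = 0.60

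These compare with 0.31 when nothing is missed. The protocol gives no value for m. The figures show sensitivity only and do not estimate the note's effect.

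**5. Direction for OS.** Assumptions, none from the protocol: exponential survival with median 6 months, a random share of subjects unobserved from 1 month before death, cut-off at 12 months. The simulated Kaplan-Meier median (200,000 subjects) is 5.97 months at a share of 0%, 6.6 at 10%, 7.3 at 20% and 8.3 at 30%. The bias is upward. Even at a given share this is a ceiling, since subjects who refuse all contact would be censored under any wording.

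**The case against.** The note can be read as a labelling instruction: it says *should*, and it tells sites which of two labels to use. Section 4.2.3 already lets a subject who only stops treatment stay in safety and survival follow-up. That much stands, so the point is confined to refusal of visits. As a mere label, though, the defence fails, because the same section attaches the end of follow-up to that label.

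A reader might infer that Cycle 1 DLTs in such subjects are never ascertained. The protocol does not support that:
- Withdrawals of consent, and treatment-related events causing discontinuation or interruption, are reported within 24 hours (6.4.4).
- SAEs are followed to resolution or stabilization even beyond participation, and the SAE reporting period is not stated to end at withdrawal (6.4.2.1).
- Subjects are told to call in abnormalities, and records of unscheduled care elsewhere are obtained (5.2).
- Additional tests may be done for safe withdrawal (4.2.3).
- A known DLT keeps the subject evaluable (4.5.4.2).
- Both Cohort 10 hypoxia events arose within hours of the first infusion (1.4), and infusions on Cycle 1 Days 1-2 and 4-5 are now inpatient (4.5.2).

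A reader might also scale a 6-month median by 1/(1−f) for f = 10% to 20%, giving 6/0.90 = 6.7 to 6/0.80 = 7.5 months, and conclude that OS is overstated by 11-25%. That does not stand either. The median and f are assumed, the formula is for an exponential rate while 7.3.2.3 specifies Kaplan-Meier, and it blames the note for subjects who would refuse all contact anyway.

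Finally, OS is one of six secondary efficacy measures in an uncontrolled Phase 1 study with no OS hypothesis. This limits the consequence but does not justify discarding obtainable data.

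**Conclusion.** The point holds in limited form. As written, 4.2.3 closes out subjects who have refused only site visits, and so loses survival status and reports of symptoms or events obtainable by telephone or from records. The loss falls mainly during treatment and at the 30-day and 3-month contacts. It is plausibly informative for OS, with bias toward longer survival, and it can leave some AEs within 30 days of the last dose uncollected.

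Its size is unknown: the protocol gives no refusal rate and no reasons for refusal. That refusers are the sickest subjects is a reasonable inference, not a documented fact. Existing safety reporting narrows the loss for SAEs and DLTs but does not restore scheduled AE collection or survival status. No stated figure is wrong. The wording should be changed.

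**What to change.** - **4.2.3:** Reserve withdrawal of consent for explicit refusal of further contact or follow-up. Record refusal of site visits as a separate disposition that keeps telephone and records-based follow-up, for AEs and SAEs to 30 days after the last dose and for survival to end of study.
- **5.2.3.2 and 5.3.7:** Allow the 3-month survival contact by telephone.
- **7.3.2.3:** Name withdrawal of consent in the OS censoring rule.
- **Cycle 1:** State that a call can identify a symptomatic DLT, which makes the subject evaluable, but does not replace the Day 8-22 laboratory tests and oximetry. A telephone-only subject without a DLT remains nonevaluable and is replaced.

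The cost is wording in these sections, one added disposition category, a few calls and possibly a line in the consent form. Subjects can still refuse all contact. Off-site contact will not recover laboratory-defined toxicity.

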4.2.4 Replacement of Subjects

In the dose-escalation phase, nonevaluable subjects, defined as any subject discontinued during the DLT evaluation period for reasons other than a DLT, will be replaced in the same dose cohort.

In the dose-expansion phase, subjects who do not complete at least 2 cycles of MEDI-565 for reasons other than disease progression or toxicity will be replaced.

4.3 Treatment Assignment

An Interactive Voice/Web Response System (IXRS) will be used to both document participation and to assign a dose cohort (dose-escalation phase), a dose level (tumor regression escalation), or a treatment arm (dose-expansion phase) to the subject. A subject is considered entered into the study when the investigator notifies the IXRS that the subject meets eligibility criteria and the IXRS provides the assignment of investigational product.

The procedure for using IXRS is as follows:

- Once the subject has signed the informed consent form, the investigator or designee contacts the IXRS and the SID number will be provided. The subject will keep this SID number throughout the study.
- After confirmation of eligibility, the investigator or designee contacts the IXRS and provides the SID number and subject's baseline characteristic(s) used to verify that it is the same subject
- The IXRS assigns a dose cohort or treatment arm to the subject
- Confirmation of this information is sent to the investigator/designee who dispenses the investigational product to the subject per the communication and records the appropriate information in the subject's medical records, site's subject screening log, and investigational product accountability log

Details for using the IXRS will be provided in the IXRS manual.

Investigational product (MEDI-565) must be administered after the dose cohort or treatment arm is assigned. If there is a delay in the administration of investigational product such that it will not be administered within the specified timeframe, the study monitor must be notified immediately (see Section 4.5.3).

4.4 Blinding

This study is not blinded.

4.5 Study Treatment

4.5.1 Investigational Product Supplies and Accountability

Investigational product will be distributed to clinical sites using designated distribution centers. MedImmune will provide the investigator(s) with adequate quantities of investigational product. All MEDI-565 materials must be stored at 2°C to 8°C (36°F to 46°F).

MEDI-565: MEDI-565 is supplied in 3 mL vials. MEDI-565 is a sterile lyophilized formulation (0.25 mg MEDI-565 per vial, 0.5 mL nominal after reconstitution). The formulation after reconstitution is 0.5 mg/mL in 30 mM sodium citrate/citric acid, 75 mM L-lysine hydrochloride, 172 mM (6.5% w/v) trehalose dihydrate, 0.02% (w/v) polysorbate 80, pH 6.0.

MEDI-565 IV Bag

Protectant: MEDI-565 IV Bag Protectant is supplied in 20 mm vials as a sterile liquid formulation. The formulation is 25 mM citric acid, 1.25 M L-lysine hydrochloride and 0.1% (w/v) polysorbate 80, pH 7.0.

The compatibility of reconstituted MEDI-565 Drug Product was demonstrated for the preparation and administration procedures described below. The results showed that administration of MEDI-565 requires the use of an IV Bag Protectant to minimize adsorption of active material to IV bag and administration set components. MEDI-565 is compatible with properly treated standard IV infusion components composed of polyethylene or polyolefin that are DEHP-free and latex-free. IV bags containing a 0.9% sodium chloride (normal saline) solution using a representative administration set with a 0.2 µm in-line filter were tested.

The investigator's or site's designated investigational product manager is required to maintain accurate investigational product accountability records. Upon completion of the study, copies of investigational product accountability records will be returned to MedImmune. All unused investigational product will be returned to a MedImmune-authorized depot or disposed of upon authorization by MedImmune or its designee.

4.5.2 Treatment Regimen

MEDI-565 will be administered by IV infusion over 3 hours per day for 5 consecutive days every 28 days (1 cycle). The starting dose will be 0.75 µg.

The proposed dose levels for MI-CP216 are detailed in [Table 4.5.2-1](#).

Criteria for stopping and restarting the infusion are described in Section [4.5.4.4](#). Treatment may be continued in subjects who have a response of SD or better, until documentation of disease progression, initiation of alternative anticancer therapy, unacceptable toxicity, or other reasons for treatment withdrawal. Cycles may be delayed for up to 7 days for management of toxicity as described in Section [4.5.4.4](#) or to accommodate scheduling issues.

Beginning with Amendment 4 and as part of the overall risk mitigation plan, subjects will be admitted for inpatient infusion of MEDI-565 starting with Cycle 1, Day 1 until completion of the infusion on Cycle 1, Day 2 and again beginning with the infusion on Cycle 1, Day 4 until completion of the infusion on Cycle 1, Day 5. Subjects may be discharged after all protocol-mandated procedures and monitoring for the given visit are complete and the subject is clinically stable. Subsequent infusions of MEDI-565 will be administered to subjects on an outpatient basis.

Table 4.5.2-1 MEDI-565 Dose Levels for Dose-escalation Cohorts and Expansion Arm

Dose Cohort	No. of Subjects	MEDI-565 Dose
1	1	0.75 µg by IV infusion over 3 hours per day for 5 days
2	1	2.25 µg by IV infusion over 3 hours per day for 5 days
3	1	6.75 µg by IV infusion over 3 hours per day for 5 days
4	1	20 µg by IV infusion over 3 hours per day for 5 days
5	3	60 µg by IV infusion over 3 hours per day for 5 days
6	3	120 µg by IV infusion over 3 hours per day for 5 days
7	3	300 µg by IV infusion over 3 hours per day for 5 days
8	3	750 µg by IV infusion over 3 hours per day for 5 days
9	3	1.5 mg by IV infusion over 3 hours per day for 5 days
10	5	3 mg by IV infusion over 3 hours per day for 5 days
11 ^a	3-6	1.5 mg by IV infusion over 3 hours per day for 5 days
12 ^a	3-6	3 mg by IV infusion over 3 hours per day for 5 days
13 ^a	3 - 6	5 mg by IV infusion over 3 hours per day for 5 days
14 ^a	3 - 6	7.5 mg by IV infusion over 3 hours per day for 5 days
15 ^a	3 - 6	10 mg by IV infusion over 3 hours per day for 5 days
Pancreatic cancer expansion	Up to 20	MTD/OBD by IV infusion over 3 hours per day for 5 days
CRC expansion	Up to 20	MTD/OBD by IV infusion over 3 hours per day for 5 days
Gastroesophageal cancer expansion	Up to 20	MTD/OBD by IV infusion over 3 hours per day for 5 days

CRC = colorectal cancer; IV = intravenous; MTD = maximum tolerated dose; OBD = optimum biologic dose.

^a All subjects enrolled in Cohort 11 or higher or in an expansion cohort will receive dexamethasone prophylaxis.

In the dose escalation phase, the minimum number of subjects (1 or 3) will enroll according to DLT rules. The maximum number of subjects includes up to 6 evaluable subjects enrolled in each cohort.

In the dose-expansion phase, 3 treatment arms of approximately 20 subjects with refractory pancreatic adenocarcinoma, 20 subjects with refractory CRC, and 20 subjects with refractory gastroesophageal cancer will receive MEDI-565 at the MTD/OBD dose by IV infusion over 3 hours per day for 5 consecutive days every 28 days.

